6.1.2 Sensitivity Analyses for Primary Outcome

No adjustments will be made for multiple testing of study parameters. Therefore, interpretation of p-values for these sensitivity analyses should be considered descriptive in nature.

The following analyses will be performed for the primary outcome:

1. The primary analyses will be repeated for the PP Analysis Set.
2. The primary analysis (t-test) will be repeated, using the mITT Analysis Set to test the hypothesis:
 - Null hypothesis: average $M\Delta$ anti- $A\beta$ 40 (ABvac40) - average $M\Delta$ anti- $A\beta$ 40 (placebo) ≤ 1.778
 - Alternative hypothesis: average $M\Delta$ anti- $A\beta$ 40 (ABvac40) - average $M\Delta$ anti- $A\beta$ 40 (placebo) > 1.778
3. The change in anti- $A\beta$ 40 antibody signal from baseline to each post-baseline efficacy visit will be analyzed using a Mixed-Model Repeated Measures (MMRM), using the mITT Analysis Set.

The MMRM will include change from baseline in anti- $A\beta$ 40 antibody signal as the dependent variable; treatment, protocol-specified visits, treatment-by-visit interaction, and amyloid positivity as the fixed effects; baseline anti- $A\beta$ 40 antibody signal and baseline age as covariates; and measures within-patient at each visit as a repeated measure. The variance-covariance matrix will be assumed to be unstructured. If the procedure does not converge then a compound symmetric variance-covariance matrix will be used instead.

The least squares (LS) mean change from baseline will be presented for each treatment group (ABvac40 and placebo) for each post-baseline scheduled visit, along with the LS mean treatment difference (ABvac40 – placebo), 95% CI for mean treatment difference and p-value for comparison of treatment groups.

The following is sample SAS® code for the MMRM:

```
proc mixed data=pp method=ml;
  class Patient Treatment Visit a_PET;
  model change = Baseline a_PET Treatment Visit age
    Treatment*Visit / s;
  repeated Visit / type=un subject=Patient r;
  lsmeans Treatment*Visit / pdiff cl;
run;
```

A plot of LS means over time will be presented by treatment group.

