Analysis for antibody titration and determination of A β peptide and cytokine levels will be carried out at Int-6m (V16) and Final visit (V25/V23) [Part A] and at V22B (Part B), once the samples from all the subjects are available. Analysis of antibody-secreting cells [Part A and Part B], cytokine-secreting cells [Part A] and the immunophenotyping [Part A] will be performed subject by subject, immediately after each visit upon receiving the sample in the laboratory.

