2.1.1 Part A

Part A of the study will last for up to 24 months (from V0 to V25) and at least 18 months (up to V23) during which randomized study participants will receive five monthly (every four weeks) immunizations plus a booster shot at month 10 (V18). During the study, two interim analyses will be performed to assess safety, tolerability and biological activity of the treatment (including data from the collected disease biomarkers). These analyses will be reviewed by an independent Data Safety Monitoring Board (DSMB).

Additionally, after all patients complete their 18-month visit (V23) of Part A, a statistical analysis will be performed to determine whether Part B of the study should be discontinued. The study scheme for Part A is shown in Figure 1.

Figure 1: AB1601 Study Schematic – Part A

[figure not shown]

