3.1 Analysis Sets

3.1.1 Intent-to-Treat (ITT) Analysis Set

The ITT Analysis Set will include all randomized patients who received any study treatment.

Analysis of all secondary efficacy endpoints will be carried out using the ITT Analysis Set. Patients will be analyzed according to their randomized treatment assignment, regardless of the treatment received.

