4.2.2 Secondary Outcome Variables

4.2.2.1 Characterization of Immune Response

- Levels of anti-keyhole limpet hemocyanin (KLH) (Part A and Part B) and anti- $A\beta$ 42 antibodies in plasma (Part A only - anti- $A\beta$ 42 antibodies in plasma are not analysed by Araclon)
- Level of anti- $A\beta$ 40 antibodies in Cerebrospinal Fluid (CSF)
- Level of anti- $A\beta$ 40 antibodies in plasma

- Analysis of the peripheral blood cell subsets by immunophenotyping – Part A only (not analysed by Araclon)
- Levels of antibody secreting cells (only analysed in Part A and not analysed in Part B)
- Levels of cytokine-secreting cells (IFN- γ and IL-4) – Part A only (samples from only a small number of patients were analyzed. Hence, data for this analysis will not be reported)

4.2.2.2 Assessment of disease biomarkers:

- Levels of A β 40 and A β 42 peptides in plasma
- Cortical fibrillary amyloid deposition assessed by a-PET scans.
- Levels of CSF biomarkers [A β 42, A β 40 (Part A and B) and Tau, P-tau, neurofilament light and neurogranin (Tau, P-tau, neurofilament light and neurogranin were only analysed in Part A and were not analysed in Part B)] and other A β peptide species (other A β peptide species were not analysed by Araclon) (Part A and Part B)
- Brain volumetric changes (including hippocampal and ventricle changes) and atrophy of the hippocampus using MRI.

4.2.2.3 Assessment of cognition and quality of life:

- Mini Mental State Examination (MMSE):
 - an 11-question measure that tests five areas of cognitive function: orientation, registration, attention and calculation, recall, and language. The maximum score is 30. A score of 23 or lower is indicative of cognitive impairment
 - the following parameters will be summarized/analyzed as outlined in section 6.3:
 - total MMSE score
- Clinical Dementia Rating (CDR) scale:
 - a 5-point scale used to characterize six domains of cognitive and functional performance applicable to Alzheimer disease and related dementias: Memory, Orientation, Judgment & Problem Solving, Community Affairs, Home & Hobbies, and Personal Care.
 - the following parameters will be summarized/analyzed as outlined in section 6.3:
 - CDR-Sum of Boxes (CDR-SB), derived as the sum of the six individual domain scores and can range from 0 to 18.

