6.1.3 Analysis of Secondary Outcome Variables

No adjustments will be made for multiple testing of study parameters. Therefore, interpretation of p-values for the analyses of secondary outcomes should be considered descriptive in nature.

The following analyses will be performed for all secondary outcomes specified in section 4.2.2 of this SAP (above), using the ITT Analysis Set:

1. The MMRM analysis described in section 6.2 will be repeated for all continuous parameters.

With the exception of levels of anti-A β 40 antibodies in CSF and plasma, the dependent variable will be the change from baseline in secondary outcome as the dependent variable; treatment, protocol-specified visits, treatment-by-visit interaction, and amyloid positivity as the fixed effects; baseline secondary outcome and baseline age as covariates; and measures within-patient at each visit as a repeated measure.

For the analysis of levels of anti-A β 40 antibodies in CSF and plasma, the dependent variable with the be recorded outcome value (i.e. not the change from baseline) and the baseline outcome covariate will be removed from the model.

The following factors may also be included in the model: ApoE carrier status, baseline use of AD symptomatic medication and clinical subgroup – MCI or vmAD, if found to be significantly associated with the response measure ($p < 0.15$).

2. A plot of LS mean change over time will be presented by treatment group.

All analysis will be repeated for baseline a-PET positive and baseline a-PET negative patients separately for the following parameters:

1. Disease biomarkers – all parameters listed in section 4.2.2.2 above.
2. Cognition assessment – MMSE, CDR-SB, RBANS, ADCS-ADL MCI, C-SSRS, IGE, EQ-5D-5L and TMT.

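### The SAP's only MMRM specification uses maximum likelihood with no small-sample degrees-of-freedom method, so its 95% intervals are modestly too narrow; the compound-symmetry fallback is a further, conditional problem

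*SAP*

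**What the plan says.** SAP 6.1.2 describes an MMRM for change in anti-Aβ40 signal and gives sample code beginning "proc mixed data=pp method=ml". The MODEL statement carries only the option that prints the solution, and the covariance is unstructured. The text adds: "If the procedure does not converge then a compound symmetric variance-covariance matrix will be used instead". An LS-mean difference, 95% CI and p-value are reported at each visit.

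SAP 6.1.3 extends the model: "The MMRM analysis described in section 6.2 will be repeated for all continuous parameters". It continues: "All analysis will be repeated for baseline a-PET positive and baseline a-PET negative patients separately for the following parameters", listing the disease biomarkers and cognition measures. The biomarkers include "Levels of A β 40 and A β 42 peptides in plasma" (SAP 4.2.2.2). It also allows three further factors (ApoE carrier status, baseline AD medication, clinical subgroup).

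Neither document names REML, Kenward-Roger, Satterthwaite or any other degrees-of-freedom method. The MMRM text in Protocol 9.1.2.2 names no estimation method.

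On follow-up, SAP 2.1.1 says "Part A of the study will last for up to 24 months (from V0 to V25) and at least 18 months (up to V23"), and Protocol 7.2.1.1 says certain assays "will be carried out at Int-6m (V16) and Final visit (V25/V23) [Part A"]. A patient may therefore finish Part A without a V25.

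**The concern.** Maximum likelihood divides the residual variation by the number of patients without deducting the fixed effects estimated, so standard errors are biased downwards. The bias is larger in smaller samples and with more covariates. With many visits, ignoring the uncertainty in an unstructured covariance matrix adds to it, and nothing in the plan corrects for that.

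The fallback raises a separate issue. Compound symmetry gives every visit the same variance. If the spread changes over time, intervals are too narrow at high-variance visits and too wide at low-variance ones.

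These are sensitivity and exploratory analyses. Even so, their treatment differences for antibody levels, biomarkers and cognition will be read with these intervals, and Protocol section 2 says such data inform the decision on Phase III.

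**Working it through.** **Figures stated by the plan.** The MMRM has no stated operating characteristic beyond the nominal 95%. The primary t-test power, which this point does not touch, reproduces: with SDs 2.0 and 1.0, difference 1.778 and one-sided 0.025, 15 per group gives 86.9% (normal approximation) or 84.4% (pooled t), against the stated 85%.

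**Inputs from the documents.** 120 patients, about 70 completers (SAP 3.2), so 70/120 = 58% at the last visit. About 50% amyloid-negative prevalence (Protocol 2.7), so about 60 patients per a-PET stratum. Post-baseline visits: PET and CSF 2, MRI volumes 3 (Protocol 7.2.1.2); cognition up to 4 (7.2.1.3); plasma outcomes 11 (7.2.1.1, if every listed blood visit is assayed).

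**Assumptions.** Random monotone dropout. Residual SD rising from 1 to 1.6 (set A) or doubling (set B). Between-subject df for ML and plain REML, because the SAP names none.

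**One-visit check.** With n patients and p between-subject parameters, ML SE / REML SE = √((n − p)/n).
- n = 120, p = 5 (intercept, treatment, baseline, age, a-PET): √(115/120) = 0.979; true error of a nominal 5% test 5.5%.
- n = 60, p = 4 (one stratum): √(56/60) = 0.966; error 5.8%.
- n = 35, p = 4 (stratum completers): √(31/35) = 0.941; error 6.4%.
- n = 60 with the three optional factors, p = 7: √(53/60) = 0.940.

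**Simulated two-sided error at the last visit, no treatment effect, planned dropout** (%: ML / REML with the same df / REML with Kenward-Roger):

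| Visits | Set A, N=120 | Set A, n=60 | Set B, N=120 | Set B, n=60 |
|---|---|---|---|---|
| 2 | 5.5/5.1/5.1 | 6.3/5.6/5.4 | 5.8/5.4/5.3 | 5.8/5.0/4.7 |
| 3 | 5.8/5.3/5.2 | 6.1/5.4/5.2 | 5.8/5.5/5.4 | 5.5/4.8/4.5 |
| 4 | 5.5/5.1/4.9 | 5.9/5.2/4.9 | 5.6/5.2/4.9 | 5.9/5.5/5.0 |
| 11 | 6.3/5.7/5.1 | 7.1/6.3/4.8 | 6.0/5.8/5.0 | not completed |

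Monte Carlo SE is about 0.3 points for set A with 2 and 3 visits and set B with 2–4 visits, and about 0.5 for set B with 11 visits. A further ML check gave 5.2% and 5.6% (2 visits, N=120 and n=60), 5.5% and 6.2% (4 visits), and 7.8% (11 visits, n=60, SE about 0.9). In set B, ML intervals were about 2–5% narrower than Kenward-Roger intervals.

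**If half of those due at V25 skip it (assumed share).**
- Set A, n=60: 7.4/6.4/5.5% (2 visits) and 9.5/7.7/6.0% (3 visits). N=120: 5.7/5.0/4.6% and 6.3/5.7/5.2%.
- Set B, 2–4 visits: ML 6.9–7.3% at N=120 and 8.7–10.6% at n=60. With 11 visits and N=120, ML gives 11.0%.

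**How often the fallback is reached** (unstructured ML not converged in 100 iterations of the simulation's own algorithm, not SAS). At planned dropout: none, for any number of visits. With half skipping V25, n=60: 1 of 5,000, 10 of 5,000, 8 of 1,000 and 154 of 300 for 2, 3, 4 and 11 visits. N=120: none for 2–4 visits, 15 of 300 for 11 visits; set B gave about 9% failures there. With a quarter skipping, 11 visits: 6 of 300 (n=60) and 0 of 300 (N=120).

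**What the fallback does** (11 visits, n=60, half skipping). Error at last/first visit in runs that fell back: 10.7/5.9% with equal SDs, 13.1/4.5% with 1.25-fold SD growth, 16.0/0.7% with 1.6-fold growth (SE about 2 at the last visit). Unstructured ML fits that converged in that setting also gave 11–17% at V25.

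**Alternatives in that setting.** Heterogeneous Toeplitz, ARH(1) and CSH, fitted by REML with first-order Kenward-Roger, gave 3.6–5.6% at the last visit and 3.6–6.4% at the first. Four to six Toeplitz fits failed; no ARH(1) or CSH fit did.

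**The case against.** The effect is small: at N=120 with 2–4 visits, ML exceeds Kenward-Roger by about 0.4–0.7 points. The p-values are declared descriptive, no decision rule uses this model, the study is not powered for these outcomes, and the block is labelled sample code. With 2–4 visits at planned dropout, ML accounts for nearly all the excess; the df method adds 0–0.5 points. The fallback matters only if V25 is sparse, the fit fails and, for its specific distortion, variances differ. Neither the skipping share nor the visit SDs are documented, and the convergence counts move with the iteration limit (154 becomes 231 of 300 at 50 iterations).

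Most of this stands as a limit on size. It does not remove the point. The descriptive label is given because multiplicity is not controlled; it does not justify intervals that miss their stated coverage. The code is labelled a sample, but the prose is silent, so nothing else would direct the programmer to another method. The V25 excess under the fallback is not unique to it, which is why it is a secondary issue here. Unstructured REML with Kenward-Roger was not run for 11 visits with half skipping, so the first step of the remedy is untested in that extreme case.

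**Conclusion.** The concern holds. As coded, the MMRM gives intervals that are modestly too narrow: error about 5.5–6.3% for 2–4 visits and 6–7% for 11 visits at planned dropout, more at V25 if attendance there is poor. Two SD patterns and a closed-form check agree on direction and approximate size. The compound-symmetry problem is conditional: it concerns mainly plasma Aβ40 and Aβ42 within an a-PET stratum, and less often the 11-visit outcomes at N=120. The sizes rest on assumed SD growth, random dropout, an even a-PET split, between-subject df and an assumed V25-skipping share. The primary t-test is not affected. The change should be made because it is nearly free and corrects the error bars on almost every exploratory treatment comparison.

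**What to change.** In SAP 6.1.2, state REML with Kenward-Roger in the text and change the code to `method=reml` with `ddfm=kr`. Replace compound symmetry with a pre-specified ordered list of heterogeneous-variance structures under the same estimation, for example heterogeneous Toeplitz, then ARH(1), then CSH. Report the number of patients contributing at V25.

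Editorial corrections:
- The dataset in the code is PP. The text requires mITT for the antibody MMRM, and for secondary outcomes SAP 3.1.1 says "Analysis of all secondary efficacy endpoints will be carried out using the ITT Analysis Set"; PP and PPc are repeats.
- In 6.1.3, the reference to section 6.2 should be to 6.1.2.
- In 4.2.2.3, the references to a non-existent section 6.3 should point to 6.1.3, and to 6.2 for the combined Part A and B summaries.

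Cost: a few words of code and text. Standard errors rise by about 2% at N=120 and 4% in one stratum for 2–3 visits, up to 7% in a stratum with 11 visits, and about 7–12% at V25 in a stratum if half skip it.

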6.1.3 Analysis of Secondary Outcome Variables

No adjustments will be made for multiple testing of study parameters. Therefore, interpretation of p-values for the analyses of secondary outcomes should be considered descriptive in nature.

The following analyses will be performed for all secondary outcomes specified in section 4.2.2 of this SAP (above), using the ITT Analysis Set:

1. The MMRM analysis described in section 6.2 will be repeated for all continuous parameters.

With the exception of levels of anti-A β 40 antibodies in CSF and plasma, the dependent variable will be the change from baseline in secondary outcome as the dependent variable; treatment, protocol-specified visits, treatment-by-visit interaction, and amyloid positivity as the fixed effects; baseline secondary outcome and baseline age as covariates; and measures within-patient at each visit as a repeated measure.

For the analysis of levels of anti-A β 40 antibodies in CSF and plasma, the dependent variable with the be recorded outcome value (i.e. not the change from baseline) and the baseline outcome covariate will be removed from the model.

The following factors may also be included in the model: ApoE carrier status, baseline use of AD symptomatic medication and clinical subgroup – MCI or vmAD, if found to be significantly associated with the response measure ($p < 0.15$).

2. A plot of LS mean change over time will be presented by treatment group.

All analysis will be repeated for baseline a-PET positive and baseline a-PET negative patients separately for the following parameters:

1. Disease biomarkers – all parameters listed in section 4.2.2.2 above.
2. Cognition assessment – MMSE, CDR-SB, RBANS, ADCS-ADL MCI, C-SSRS, IGE, EQ-5D-5L and TMT.

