Additionally, after all patients complete their 18-months visit (V23), a statistical analysis will be performed to determine whether the Part B of the study should be discontinued.

Within the first week (3 ± 3 days) after each vaccination visit, a telephone control interview will take place.

Two weeks after each vaccination, and at 40, 50, 77 and 104 weeks there will be a safety visit consisting on:

- Physical and neurological examination (assessment of vital signs; electrocardiogram in five visits: V0, V16, V21, V23 and the final visit (V25); body biometrics; collection of adverse events and concomitant medication) at all face to face visits (V0, V1, V3, V4, V6, V7, V9, V10, V12, V13, V15, V16, V17, V18, V20, V21, V23 and V25; and PDV, if applicable).
- Blood collection for safety control and measurement of biological activity at visits: V0, V1, V3, V6, V9, V12, V15, V16, V17, V20, V21, V23 and V25
- A MRI at visits V0, V9, V16, V17, V21 and V25.

At the screening visit (V0), the participants will receive an amyloid-PET scan. Subjects will undergo additional amyloid-PET scan at V21 and final visit (V25) for the assessment of amyloid burden. The subject will receive lumbar puncture for CSF analysis at baseline (V1), V21 and at the final visit (V25) for the assessment of changes in CSF biomarkers.

Part B:

The Part B of the study will last for 18 months (from V1B to V22B). The scheme of visits will mirror the Part A scheme.

The first visit of Part B (V1B) will take place at least 18 months after the patient started Part A (i.e. he/she should have completed V23 of Part A to enter Part B).

The patients randomized to the placebo group during Part A will receive five monthly (every four weeks) immunizations with ABvac40 plus a booster shot after 6 months (Delayed start group), whereas the patients randomized to the Verum group during Part A will receive placebo following this schedule, except in V13B, where they will receive an ABvac40 booster shot

(Booster group). Given the extended inclusion period of Part A, the V13B booster will take place at different timepoints relative to the patients' last immunization. For the analysis, they will be grouped in 2 periods: 12 ± 3 months and 18 ± 3 months after their last Part A immunization.

Within the first week (3 ± 3 days) after each vaccination visit, a telephone control interview will take place.

Two weeks after each vaccination, and at 40 and 50 weeks there will be a safety visit consisting on:

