The analysis of ABvac40 biological activity – carried out in the ITT population (24 patients) – showed a significant difference between groups of treatment at the final visit only for the mean optical density (OD) without pre-adsorption (representing level of anti-A β 40 antibodies): median of 2.67 (range, 0.7-4.1) in the ABvac40 group and median of 0.60 (range, 0.6-1.3) in the placebo group (p=0.0129). Although the level of response had a considerable individual component as could be expected, 87.5 % of patients in the verum group were considered responders (those which, at any visit, showed a 3 standard deviations (SD) increase in OD with regard to the pre-immune sample) a figure which reached 91 % of the population that received the 3 immunization shots in the amended protocol. The Mean OD with pre-adsorption indicates that over 95% of the signal registered in the plasma samples from the patients treated with verum was due to the presence of specific anti-A β 40 antibodies.

The other parameters of biological activity analyzed did not were significant different between the two groups of treatment at the final visit.

In summary, the clinical trial was considered satisfactory because the average frequency of AEs (overall or grouped as neurological, psychiatric or cardiovascular) was not significantly different between the group that received the active treatment (ABvac40) and the placebo group. In fact, the incidence of AEs tended to be lower in the active treatment group,

particularly with regard to the Neurological and Cardiovascular events. Therefore, the active treatment (ABvac40) shows a good safety and tolerability profile.

Additionally, the first interim analysis of the present ongoing Phase II clinical trial was conducted in July 2019, after the first 36 patients have completed their 24-week visit. The results showed that ABvac40 has a favorable profile concerning futility criteria, safety and immunogenicity data, encouraging the amendment of the study protocol to include the delayed-start extension (Part B).

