CSF Analysis		Cells Total Proteins Glucose Levels of A β 1-40, A β 1-42; Total tau and Phosphorylated tau	Special Lab

If sample collected for laboratory analyses are non-analyzable or non-reportable due to various factors, they will need to be recollected by contacting the subject for unscheduled visit(s) so that additional samples (blood, urine) can be collected from subjects and assayed for critical analytes at any study time point. In this case, the data from the last sample analyzed at the corresponding study time point will be recorded in the eCRF.

Backup sample of blood will be collected at screening visit (V0). This sample will be used together with sample from baseline visit (V1) to assess pre-treatment levels of critical analytes.

Samples will be stored/retained in the Araclon-Grifols facilities for additional or repeated analysis until Araclon-Grifols deems that all analysis in support of the study have been completed. After this period, the samples will be destroyed. If an additional, not related with the initially programmed analysis is intended subjects will be requested to extend their informed consent.

Biological samples will be managed according to local regulations of each participating country. Araclon-Grifols will comply with all pertinent legislation to maintain the confidentiality of all health-related information obtained in the study.

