9.2 Changes to protocol specified analyses

The definition of the ITT analysis set was changed from the protocol to the SAP and a mITT analysis set was introduced. In addition, the SAP specifies that the mITT analysis set will be used for the analysis of the primary endpoint and the ITT analysis set will be used for the analysis of all secondary efficacy endpoints.

The definition of the mITT analysis set is identical to the definition of the ITT analysis set in the protocol, ensuring that the population of patients entering the analysis of the primary endpoint remains as planned in the protocol.

The ITT analysis set was redefined in the SAP to remove the restriction of patients requiring a baseline and at least one post-baseline anti-Ab40 antibody assessment. This is to ensure that valid data from secondary endpoints are not excluded from the analysis, based on the availability of primary endpoint assessments.

Additional per-protocol analysis sets were introduced.

The Part A PPc Analysis Set comprising of all patients in the ITT Analysis Set who received all doses of study medication (on V1, V4, V7, V10, V13 and V18), have attended the safety visit after booster (V20), have no major protocol deviations that could affect the efficacy analyses or major protocol deviations that have been classified as “Use of disallowed concomitant medication”, relating to use of Anti-Alzheimer Disease medication.

The Part B PPc Analysis Set will comprise of all patients in the ITT Analysis Set who received all doses of study medication (on V1B, V4B, V7B, V10B, V13B and V18B in Part B), have attended the safety visit after booster (V20B in Part B), have no major protocol deviations that could affect the efficacy analyses or major protocol deviations that have been classified as “Use of disallowed concomitant medication”, relating to use of Anti-Alzheimer Disease medication.

The PPc Analysis Sets will be used for the sensitivity analysis of secondary efficacy endpoints relating to the assessment of cognition and quality of life, while the PP Analysis Sets will be used for the sensitivity analysis of the primary efficacy endpoint and secondary efficacy endpoints relating to the characterization of immune response and the assessment of disease biomarkers.

Level of anti-A β 40 antibodies in plasma has been added as a secondary outcome, to further characterize immune response.

Table 2-3 presents variables those were not analyzed by the Araclon or vendor:

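### SAP 6.1.3 drops the collected baseline from the plasma and CSF anti-Aβ40 level models without recording or justifying the departure, which can cost some precision

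*SAP*

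**What the plan says.** SAP 6.1.3 applies the MMRM to all continuous secondary outcomes in the ITT set. The general form has change from baseline as response, with the baseline value and age as covariates. Anti-Aβ40 levels in CSF and plasma are a declared exception: the response is the recorded value and "the baseline outcome covariate will be removed from the model". No reason is given. The same section says that "interpretation of p-values for the analyses of secondary outcomes should be considered descriptive in nature".

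Elsewhere the plan adjusts for baseline:

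- SAP 6.1.1: the ANCOVA of the maximal increment has baseline OD as covariate.
- SAP 6.1.2: the MMRM of the plasma signal, in the mITT set, takes baseline "antibody signal and baseline age as covariates".
- Protocol 9.1.2.2: the MMRM covers all primary and secondary efficacy variables, with change as response and the baseline score among the fixed effects. CSF anti-Aβ40 is one of those variables (Protocol 7.1.1.2).

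Baseline is collected. Protocol 7.2.2 says of the V0 backup blood sample: "This sample will be used together with sample from baseline visit (V1) to assess pre-treatment levels of critical analytes". CSF is taken at V1, V21 and V25.

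SAP 9.2 records that the plasma level "has been added as a secondary outcome, to further characterize immune response". It does not record that the baseline term was removed from either model.

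**The concern.** A pre-treatment measurement of the outcome is usually the covariate most worth having. Leaving it out puts any stable between-patient background into the residual, and a chance difference in baseline between the arms passes into the estimated treatment difference. Here the measurement is already in hand, the protocol asks for it, and the comparable plasma antibody outcome, anti-KLH, keeps it.

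A second issue depends on what level means. If it is OD, as Protocol 2.2 suggests when it uses OD to represent the antibody level, then SAP 6.1.2 and 6.1.3 fit two MMRMs to one signal. One is adjusted in mITT and the other unadjusted in ITT, and the plan does not say which to prefer if they differ.

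**Working it through.** **The plan's own figure.** Inputs from Protocol 9.2: difference 1.778 OD, SDs 2.0 and 1.0, one-sided 0.025. The average variance is (2.0² + 1.0²)/2 = 2.5, so the SD is 1.581. For 85% power, n per arm = 2 × 2.5 × (1.960 + 1.036)² / 1.778² = 14.2, rounded up to 15. This matches Protocol 2.6. At 35 per arm the t-test power is 99.6%, consistent with the stated figure of more than 85%. None of this involves the 6.1.3 model.

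**Precision formula.** With correlation ρ between baseline and post-baseline level, the SE without baseline divided by the SE with it is 1/√(1 − ρ²). This is a single-visit approximation. The documents give no ρ, so the range is assumed:

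| ρ | SE ratio | Effective n out of 70 |
|---|---|---|
| 0 | 1.000 | 70 |
| 0.1 | 1.005 | 69.3 |
| 0.2 | 1.021 | 67.2 |
| 0.3 | 1.048 | 63.7 |
| 0.5 | 1.155 | 52.5 |
| 0.7 | 1.400 | 35.7 |

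**Where plasma OD is likely to fall.** The only spread for unvaccinated patients is Phase I at the final visit: "median of 0.60 (range, 0.6-1.3) in the placebo group". Phase I had 8 placebo patients. The median equals the minimum, so about five of the 8 are near 0.6 and the other three are at most 1.3.

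- Widest such sample: five at 0.6 and three at 1.3, with mean (3.0 + 3.9)/8 = 0.8625.
- Sum of squares: 5 × 0.2625² + 3 × 0.4375² = 0.919. SD = √(0.919/7) = 0.36.
- Take 0.36 as the baseline SD, and let level = baseline + change, with change independent of baseline and variance 2.5.
- ρ = 0.36/√(0.131 + 2.5) = 0.22. SE ratio = √(2.631/2.5) = 1.026.

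The SE is therefore about 2.6% wider. For other baseline SDs the ratio is 1.002 at 0.1 OD, 1.018 at 0.3, 1.049 at 0.5 and 1.183 at 1.0.

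**Chance imbalance.** With 35 per arm and SD 0.36, the baseline difference between arms has SE 0.36 × √(2/35) = 0.09 OD. In this additive model it passes unadjusted into the treatment difference.

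**Level or change as response.** Once baseline is in the model, subtracting it from the response only shifts its coefficient by 1. In one simulated data set (70 patients, baseline SD 0.3) both responses gave a difference of 1.938 with SE 0.342. The level without baseline gave 2.030 with SE 0.346. So restoring baseline makes the 6.1.3 plasma model agree with 6.1.2 if level is OD, apart from the analysis set and any optional factors that 6.1.3 allows.

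**CSF.** The documents give no spread or correlation for CSF antibody, so no size can be derived.

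**The case against.** The strongest reply is that the exception is deliberate and may be right. The SAP lists the OD signal and the plasma level as separate outcomes. The scale of level is unsettled: Protocol 2.2 points to OD, Protocol Table 8 and SAP 6.2 speak of concentration, and Protocol 7.2.1.2 has CSF antibody determined by titration ELISA. A titer as defined in Protocol 9.1.2.1 is already referred to the pre-immune sample, so it has no useful pre-treatment value of its own. This stands as far as it goes: the two-models point holds only if level is OD, and a reader who infers a plain contradiction between 6.1.2 and 6.1.3 goes beyond the documents. It does not explain why the SAP gives no reason, or why pre-treatment OD could not serve as the covariate.

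A reader might also infer a large loss. Correlations of 0.3 to 0.6 would be worth 10% to 56% more patients, since 1/(1 − ρ²) runs from 1.10 to 1.56. The documents do not support that. The 0.6-1.3 range is from the final visit, not baseline, and it is a single cross-section, so it cannot show that background persists within patients. The plan's own SDs point to a ρ of about 0.2.

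Nor does the omission bias the comparison: allocation is randomised, and the unadjusted interval already allows for chance imbalance. The p-values are descriptive, and plasma OD is analysed with baseline in 6.1.1 and 6.1.2. All of that stands, and it keeps the point small.

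Finally, adding baseline is not entirely free. SAP 9.2 says that the ITT set was redefined so that patients are not lost from secondary analyses for want of antibody assessments, and a plain covariate would drop those without a baseline value. This is a real cost, but it can be met in the model.

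**Conclusion.** The point holds as a small improvement and a documentation gap. SAP 6.1.3 removes a collected baseline that Protocol 9.1.2.2 specifies, and SAP 9.2 does not record it. The departure is direct for CSF, a protocol-listed variable. For plasma, the level is an SAP addition to which the protocol's rule for all efficacy variables would naturally extend.

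For plasma OD the SE is about 2-3% wider. That rests on three assumptions: the Phase I final-visit placebo spread stands in for baseline spread, change is independent of baseline, and the SDs planned for the maximal increment apply at single visits. The loss is nil if baselines sit at the floor, and about 15% in the SE if ρ is 0.5. For CSF the size is unknown. There is no bias and no effect on the primary test, sample size or power. The claim of two differently adjusted models of one signal is conditional on level being OD.

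**What to change.** In SAP 6.1.3, keep the pre-treatment value and its interaction with visit as covariates in both anti-Aβ40 models. The outcome can stay on the recorded scale. Then:

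- Define level for plasma and for CSF (OD, titer or concentration). If it is a titer referred to the pre-immune sample, use the pre-treatment OD as the covariate.
- Keep patients without a baseline value by entering baseline as a response with a common mean across arms. If the covariate is on another scale, use a simple baseline imputation. In plasma few should be affected, because SAP section 3 takes the last value before first dose and V0 backs up V1.
- State how values below quantification are handled. The protocol's rule sits under laboratory safety in 9.1.3.2 and is not repeated in the SAP.
- Say whether the baseline visit is among the modelled visits.
- If the omission is kept, record it in SAP 9.2 with a reason.

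Two small tidy-ups belong in the same edit. The section asks for all secondary outcomes that "A plot of LS mean change over time will be presented by treatment group", which does not fit a recorded-value model. It also points to section 6.2 for the MMRM, which is in 6.1.2.

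The cost is one extra term with its interaction in two models and a few sentences of text. No new data are needed.
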